14.3 Analysis plan

Summary tables describing the patient cohort will be compiled, including:

- Demographics (age, sex, race, ethnicity, smoking history, recent weight loss)
- Disease history (current stage, tumor sites, histology)
- Comorbidities at start of therapy (cardiac, pulmonary, other)
- PD-L1 expression status

Analysis of primary endpoints:

- The OS curve, median OS, and a 90% confidence interval for the median OS will be estimated by standard methods (the Kaplan-Meier method for survival, and the Greenwood variance formula applied to log-transformed survival) in the efficacy cohort (primary analysis) and safety cohort (sensitivity analysis). Durvalumab will be considered a promising therapy in this population if the estimated median OS is 9 months or greater, and/or the lower bound of a 90% confidence interval for the median OS is greater than 5 months. However, these results will be interpreted in the context of safety data and the presence of durable responses attributed to study therapy.).
- All adverse events that are determined to be possibly, probably or definitely related to treatment will be tabulated according to grade and type, in order of frequency in the safety cohort. Each adverse event will be counted only once per patient, with the highest grade recorded. Serious adverse events and adverse events of special interest (ASEI, defined in section 8.1.3) will also be tabulated by frequency. Listings will be provided for all on-study deaths and adverse events that lead to withdrawal from study.

Lilenbaum et al (2008) observed a rate of grade ≥ 3 adverse events of 41% (90% CI 31%-53%) for a platinum-based doublet, and 27% (90% CI 18%-38%) for erlotinib. In this context of balancing expected toxicity and efficacy, a rate of grade ≥ 3 treatment related adverse events of 30% or less would be acceptable, especially if associated with efficacy in individuals. In a cohort of n=50, a 30% rate of grade ≥ 3 adverse events would have a 90% CI of (21%-41%), demonstrating it is likely more tolerable than the platinum doublet.

Secondary Objectives:

HCC #:16-054

Version Date: 008/11/2020

- PFS will be evaluated using the same methodology as for OS. PFS and OS will be evaluated in the unselected populations and based on PD-L1 status. The ORR and OS12 will be estimated with a 90% Wilson Score confidence interval, for the unselected population and based on PD-L1 status. HRQL at baseline, the end of each cycle, and at the end of therapy will be assessed using the FACT-L questionnaire ([name]., 2007). Total scores and subscales will be summarized for each patient, and analyzed using standard linear mixed models methods and generalized estimating equations. The primary analysis will summarize baseline QOL, average changes over the first two cycles of treatment, and average QOL in survivors at approximately 6 months and 12 months.

REFERENCES

7. EuroQol G: EuroQol--a new facility for the measurement of health-related quality of life. *Health policy (Amsterdam, Netherlands)* 1990, 16:199-208.

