1. OBJECTIVES

1.1 Primary Objectives

- To estimate overall survival (OS) with durvalumab in advanced NSCLC patients with an ECOG PS2.
- To estimate the safety of durvalumab in NSCLC patients with PS2 as determined by grade ≥ 3 treatment related adverse events.

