Study D4191C00003/ATLANTIC: The safety profile of durvalumab monotherapy in Study CD-ON-durvalumab-1108 is generally consistent with that of Study D4191C00003/ATLANTIC in subjects with locally advanced or metastatic non-small-cell lung cancer (NSCLC) treated with durvalumab 10 mg/kg Q2W. As of 05May2015, 264 of 303 subjects (87.1%) reported any AE in Study D4191C00003/ATLANTIC. Overall, events reported in $\geq 10\%$ of subjects were dyspnea (18.8%), fatigue (17.8%), decreased appetite (17.5%), cough (14.2%), pyrexia (12.2%), asthenia (11.9%), and nausea (11.2%). Nearly two-thirds of the subjects experienced AEs that were Grade 1 or 2 in severity and manageable by general treatment guidelines as described in the current durvalumab study protocols. Grade 3 or higher AEs were reported in 107 of 303 subjects (35.3%). A total of 128 subjects (42.2%) reported AEs that were considered by the investigator as related to investigational product. Treatment-related AEs (all grades) reported in $\geq 2\%$ of subjects were decreased appetite (6.6%); fatigue (5.9%); asthenia (5.0%); nausea (4.6%); pruritus (4.3%); diarrhea, hyperthyroidism, hypothyroidism, and pyrexia (3.3% each); rash (2.6%); weight decreased (2.3%); and vomiting (2.0%). Treatment-related Grade 3 AEs reported in ≥ 2 subjects were pneumonitis (3 subjects) and increased GGT (2 subjects). There was no treatment-related Grade 4 or 5 AEs. Ninety-four of 303 subjects (31.0%) reported any SAE. SAEs that occurred in $\geq 1.0\%$ of subjects were

HCC #:16-054

Version Date: 008/11/2020

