dyspnea (6.6%); pleural effusion, general physical health deterioration (2.3% each); pneumonia (2.0%); hemoptysis, pulmonary embolism (1.3% each); and pneumonitis, respiratory failure, disease progression (1.0% each). Nine subjects had an SAE considered by the investigator as related to durvalumab. Each treatment-related SAE occurred in 1 subject each with the exception of pneumonitis, which occurred in 3 subjects. Fifteen of 303 subjects (5.0%) have died due to an AE (pneumonia [3 subjects]; general physical health deterioration, disease progression, hemoptysis, dyspnea [2 subjects each]; pulmonary sepsis, respiratory distress, cardiopulmonary arrest [verbatim term (VT)], hepatic failure, and sepsis [1 subject each]). None of these events was considered related to durvalumab. Twenty-three of 303 subjects (7.6%) permanently discontinued durvalumab treatment due to AEs. Events that led to discontinuation of durvalumab in ≥ 2 subjects were dyspnea, general physical health deterioration, and pneumonia. Treatment-related AEs that led to discontinuation were increased ALT and increased hepatic enzyme, which occurred in 1 subject each.

Efficacy

Study CD-ON-durvalumab-1108: Overall, 456 of 694 subjects treated with durvalumab 10 mg/kg Q2W were evaluable for response (defined as having ≥ 24 weeks follow-up, measurable disease at baseline, and ≥ 1 follow-up scan, or discontinued due to disease progression or death without any follow-up scan). In PD-L1 unselected patients, the objective response rate (ORR), based on investigator assessment per Response Evaluation Criteria in Solid Tumors (RECIST) v1.1, ranged from 0% in uveal melanoma ($n = 23$) to 20.0% in bladder cancer ($n = 15$), and disease control rate at 24 weeks (DCR-24w) ranged from 4.2% in triple-negative breast cancer (TNBC; $n = 24$) to 39.1% in advanced cutaneous melanoma ($n = 23$). PD-L1 status was known for 383 of the 456 response evaluable subjects. Across the PD-L1-positive tumors, ORR was highest for bladder cancer, advanced cutaneous melanoma, hepatocellular carcinoma (HCC; $n = 3$ each, 33.3% each), NSCLC ($n = 86$, 26.7%), and squamous cell carcinoma of the head and neck (SCCHN; $n = 22$, 18.2%). In the PD-L1-positive subset, DCR-24w was highest in advanced cutaneous melanoma ($n = 3$, 66.7%), NSCLC ($n = 86$, 36.0%), HCC and bladder cancer ($n = 3$ each, 33.3% each), and SCCHN ($n = 22$, 18.2%).

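### No all-cause grade 3 or higher adverse event rate is planned, so the 30% tolerability criterion rests on investigator attribution and may not match its 41% benchmark

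*Combined protocol and SAP*

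**What the plan says.** The primary safety objective (Section 1.1) is to estimate safety "as determined by grade ≥ 3 treatment related adverse events". Section 14.3, repeated in substance in the Synopsis, plans one table with a grade breakdown: "All adverse events that are determined to be possibly, probably or definitely related to treatment will be tabulated according to grade and type". Each event counts once per patient at its highest grade.

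Two further outputs follow, neither with a relatedness restriction: "Serious adverse events and adverse events of special interest (ASEI, defined in section 8.1.3) will also be tabulated by frequency" and "Listings will be provided for all on-study deaths and adverse events that lead to withdrawal from study".

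The acceptability statement is that "a rate of grade ≥ 3 treatment related adverse events of 30% or less would be acceptable". Its context is a cited randomised trial that "observed a rate of grade ≥ 3 adverse events of 41% (90% CI 31%-53%) for a platinum-based doublet", with 27% for erlotinib. Neither of those rates is described as treatment-related.

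Section 8.3 records the maximum grade and an investigator causality rating for every adverse event. Section 8.3.2 requires serious events to be reported whatever their cause.

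**The concern.** Every patient receives durvalumab and the person rating causality knows it. There is no control arm against which to calibrate those ratings, and no independent causality review is described. In patients with performance status 2 and advanced lung cancer, fatigue, appetite loss and breathlessness can come from the disease or from the drug, so attribution is often uncertain.

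A related-only rate is a legitimate endpoint, but it should be readable next to the all-cause rate. Here the second figure is not planned. Two things are at stake: whether a reader can see how much the 30% criterion depends on attribution, and whether the inference that durvalumab is more tolerable than a platinum doublet compares like with like.

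**Working it through.** **1. The plan's own interval.** Section 14.3 gives a 90% interval of 21% to 41% for a 30% rate in 50 patients. Wilson score, x = 15, n = 50, p = 0.30, z = 1.645, z² = 2.706:

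- Centre: (p + z²/2n) / (1 + z²/n) = (0.30 + 0.02706) / 1.0541 = 0.3103.
- Half-width: z/(1 + z²/n) × √(p(1−p)/n + z²/4n²) = 1.5605 × √(0.0042 + 0.00027) = 0.1043.
- Interval: 20.6% to 41.5% (41.46% before rounding to one decimal), which agrees with the plan to the whole percent.

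The figure is right. The issue is which events enter the numerator.

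**2. Where each kind of grade 3 or higher event would appear.**

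| Event | Planned output |
|---|---|
| Judged related | Table by grade and type |
| Unrelated, serious | Serious-event frequency table (grade not stated) |
| Unrelated, non-serious, of special interest | Special-interest frequency table (grade not stated) |
| Fatal, or leading to withdrawal | Listing |
| Unrelated, non-serious, not of special interest, no withdrawal | None |

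Section 8.2.1 says a grade 3 event need not be serious, so the last row is not empty by definition. Fatal and immediately life-threatening events are serious under Section 8.1.2, so that row should be mostly grade 3. The other rows do not add up to a patient-level all-cause rate either: the frequency tables are not stated to be by grade, and one patient can appear in several outputs.

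**3. Size of attribution within one study.** Section 2.2.2 reports the durvalumab NSCLC study (303 patients):

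| | All-cause | Judged related | Difference |
|---|---|---|---|
| Any adverse event | 264 (87.1%) | 128 (42.2%) | 136 (44.9%) |
| Any serious event | 94 (31.0%) | 9 (3.0%) | 85 (28.1%) |
| Grade 3 or higher | 107 (35.3%) | total not given | not available |

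For the last row, the documents list only related grade 3 events seen in at least 2 patients (pneumonitis 3, raised GGT 2) and say there were no related grade 4 or 5 events. A total cannot be built from that.

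**4. How much the serious-event table would miss.** In that study 107 patients had a grade 3 or higher event and 94 had a serious event.

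- Patients with a grade 3 or higher event and no serious event number at least 107 − 94 = 13 (13/303 = 4.3%).
- The 15 patients who died of an adverse event belong to both groups, so the number is at most 107 − 15 = 92 (92/303 = 30.4%).
- Scaled to 50 patients: 50 × 13/303 = 2.1 to 50 × 92/303 = 15.2.

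Some of these patients would still be picked up by the related-event table, the special-interest table or the withdrawal listing. The number of patients with a grade 3 or higher event but shown in no output is therefore smaller, and could be close to zero at the lower end. The scaling assumes a similar event pattern in PS2 patients, which the documents do not establish.

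**5. Direction of the benchmark mismatch.** Patients with a related grade 3 or higher event are a subset of those with any such event, so the related rate cannot exceed the all-cause rate. If the 41% is all-cause, setting a related-only durvalumab rate against it understates durvalumab's toxicity by the gap between its two rates. If the 41% is treatment-related, this mismatch does not arise.

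**The case against.** The plan is internally consistent. The objective is defined on related events and the table reports that endpoint. The 30% figure guides interpretation and is not a formal test. Counting possibly related events is a broad rule that limits under-attribution. Section 7 and Appendix D direct that events of interest without another cause be treated as immune-related, and Section 13.1 has safety data reviewed monthly. All of this stands, and it is why the endpoint should not change.

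A reader might infer that the whole safety output is filtered by relatedness, and cite the 15 deaths from adverse events in the NSCLC study, of which Section 2.2.2 says "None of these events was considered related to durvalumab". The documents do not support that. On-study deaths are listed whatever their cause, and the serious-event table carries no relatedness limit, so deaths of this kind would be visible. Nor is the all-cause rate out of reach: it is unplanned, but the data for it are collected.

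It is also fair to say that an all-cause table does not remove judgement. Section 8.3 keeps events unequivocally due to progression out of adverse event reporting, and that decision is itself the investigator's.

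What the objection does not answer is the benchmark. Nothing in the plan says whether the 41% is all-cause or related, and only one of those two readings matches the planned durvalumab rate.

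**Conclusion.** The point holds as a reporting gap that is cheap to close. It is not a flaw in the primary endpoint. No all-cause grade 3 or higher rate is planned, the 30% criterion depends on unblinded attribution, and the comparison with 41% may be uneven in durvalumab's favour.

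The size for this trial is unknown. The same-study contrasts (87.1% against 42.2%; 94 serious cases against 9) show that attribution can shift rates substantially, but they concern any event and serious events, not the primary endpoint, and that study is not stated to be a PS2 cohort.

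A reader might go further and infer that attribution alone could carry the observed rate across 30%, by setting the related grade 3 or higher rate of 9.4% (65/694) against the all-cause 35.3%. With 50 patients, the chance of 15 or fewer is above 99.9% at 9.4% and about 27% at 35.3%. The documents do not support that inference. The two rates come from different studies, one in mixed solid tumours and one in NSCLC, and the second calculation applies a limit set for related events to an all-cause rate. Section 2.3 also cites 6% for related events in NSCLC. Starting from 9.4%, or about 5 of 50, exceeding the limit (16 of 50) would take about 11 more patients reclassified as related. The binomial contrast is illustration at most.

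**What to change.** Leave the primary endpoint and the 30% criterion as they are. In Section 14.3 and the Synopsis:

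- Add a table of all treatment-emergent adverse events regardless of causality, by worst grade per patient, in the safety cohort, next to the related-only table.
- Report the patient-level all-cause grade 3 or higher rate with a 90% Wilson interval as a supportive analysis.
- State whether the 41% doublet rate (and the 27% erlotinib rate) is all-cause or treatment-related, and compare it with the durvalumab rate of the same kind. If the source does not settle this, say so and show both durvalumab rates.
- Note under the table that events unequivocally due to progression are excluded under Section 8.3.
- Say how the yes/no causality rating collected under Section 8.3 maps to the possible, probable and definite categories used in Section 14.3, since that mapping decides which events count as related.

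The cost is one table, one interval and some wording, all from data already collected. The drawback is a less favourable figure beside the primary one, which will need a sentence of interpretation because it includes events caused by the underlying disease.

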- The OS curve and a 90% confidence interval for the median OS will be estimated by standard methods (the Kaplan-Meier method for survival, and the Greenwood variance formula applied to log-transformed survival). Prior phase II/III clinical trials have demonstrated a median OS of about 5 months with single agent therapy in PS2 patients with advanced NSCLC (Lilenbaum et al. 2005; Lilenbaum et al. 2008; Zukin et al. 2013). A median OS of 9 months with durvalumab would demonstrate a clinically meaningful improvement over the historical control median OS of 5 months with single agent therapy. Assuming 18 months of accrual with 6 months of follow-up, N=50 patients would be required to have 85% power for a 90% confidence interval for median survival to exclude 5 months (and 78% power for a 95% confidence interval).
- Safety will be summarized for all patients who receive at least one dose of study drug. All adverse events that are determined to be possibly, probably or definitely related to treatment will be tabulated according to grade and type, in order of frequency. Each adverse event will be counted only once per patient, with the highest grade recorded. Serious adverse events and adverse events of special interest (ASEI, defined in section 8.1.3) will also be tabulated by frequency. Listings will be provided for all on-study deaths and adverse events that lead to withdrawal from study. A rate of grade ≥ 3 treatment related adverse events of 30% or less would suggest that durvalumab is more tolerable than a platinum doublet in this population [Lilenbaum et al. 2008].

- **Secondary Objectives:**

- PFS will be evaluated using the same methodology as for OS. PFS and OS will be evaluated for all patients and for subgroups by PD-L1 status. The ORR and OS12 will be estimated with a 90% Wilson Score confidence interval, for all patients and based on PD-L1 status. HRQL at baseline, the end of each 4-week cycle, and at the end of therapy will be assessed using the FACT-L v4 questionnaire (Cella, 2007). Total scores and subscales will be summarized for each patient, and analyzed using standard linear mixed models methods and generalized estimating equations. The primary analysis will summarize baseline QOL, average change over the first two cycles of treatment, and average QOL in survivors at approximately 6 months and 12 months.

TABLE OF CONTENTS

Synopsis	2
TABLE OF CONTENTS	5
abbreviations and definition of terms	7
1. OBJECTIVES	11

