6.4 Duration of Therapy

Treatment may continue for up to 12 months (maximum 12 doses) or until one of the criteria for durvalumab discontinuation is met.

Permanent discontinuation of durvalumab

An individual subject will not receive any further investigational product if any of the following occur in the subject in question:

- Confirmation of PD and investigator determination that the subject is no longer benefiting from treatment with durvalumab
- Withdrawal of consent or lost to follow-up
- Adverse event that, in the opinion of the investigator or the sponsor, contraindicates further dosing
- Subject is determined to have met one or more of the exclusion criteria for study participation at study entry and continuing investigational therapy might constitute a safety risk
- Pregnancy or intent to become pregnant
- Any AE that meets criteria for discontinuation as defined in Appendix D.
- Grade \geq 3 infusion reaction
- Subject noncompliance that, in the opinion of the investigator or sponsor, warrants withdrawal; eg, refusal to adhere to scheduled visits

HCC #:16-054

Version Date: 008/11/2020

- Initiation of alternative anticancer therapy including another investigational agent

Subjects who are permanently discontinued from further receipt of investigational product, regardless of the reason (withdrawal of consent, due to an AE, other), will be identified as having permanently discontinued treatment.

Subjects who are permanently discontinued from receiving investigational product will be followed for safety per Appendix E or F, unless consent is withdrawn or the subject is lost to follow-up or enrolled in another clinical study. All subjects will be followed for survival. Subjects who decline to return to the site for evaluations will be offered follow-up by phone at months 2, 3, 4, 6, 8, 10, 12 after stopping treatment, and then every 2 months after that as an alternative.

Withdrawal of consent

If consent is withdrawn, the subject will not receive any further investigational product or further study observation.

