6.5 Duration of Follow Up

Patients will be followed for 12 months after discontinuation of study therapy or until death, whichever occurs first. Patients discontinuing study therapy for unacceptable adverse event(s) will be followed at least until resolution or stabilization of the adverse event (Appendix E).

At the discretion of the sponsor-investigator (or sponsor/investigator) the study may be closed prematurely.

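### OS12 gets a simple-proportion interval with no rule for patients censored before month 12; define it as the Kaplan-Meier 12-month estimate and keep the Wilson limits (minor)

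*Combined protocol and SAP*

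**What the plan says.** The synopsis and section 14.3 treat OS12 together with the response rate. Section 14.3 reads "The ORR and OS12 will be estimated with a 90% Wilson Score confidence interval", for the unselected population and by PD-L1 status, and the synopsis reads "The ORR and OS12 will be estimated with a 90% Wilson Score confidence interval, for all patients and based on PD-L1 status". Section 1.2 describes OS12 only as the rate of 12-month survival.

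For OS itself, 14.3 specifies "the Kaplan-Meier method for survival, and the Greenwood variance formula applied to log-transformed survival", and adds that "PFS and OS will be evaluated in the unselected populations and based on PD-L1 status".

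On follow-up, section 6.4 states "All subjects will be followed for survival" and section 6.5 states "Patients will be followed for 12 months after discontinuation of study therapy or until death". Appendices E and F schedule survival contacts up to and beyond 12 months after the last dose, with telephone contact for patients who will not return but agree to be called. Section 14.3 also plans a summary of "average QOL in survivors at approximately 6 months and 12 months".

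Observation can still end early. Section 6.4 states "If consent is withdrawn, the subject will not receive any further investigational product or further study observation" and lists loss to follow-up. Section 6.5 allows premature closure at the sponsor-investigator's discretion.

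**The concern.** A Wilson interval in its usual form needs a count alive at 12 months and a denominator of patients whose status at 12 months is known. For the response rate that is natural. For OS12 it works only if nobody counted is censored before month 12, and the plan does not say what to do with anyone who is. Such a patient could be counted as dead, dropped or counted as alive. The choice would be open after the data are seen.

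The report would also carry two 12-month survival figures from the same data, one from the proportion and one read off the Kaplan-Meier curve, overall and in each PD-L1 subgroup. They agree for certain only without early censoring. At stake is the accuracy and consistency of a secondary estimate.

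**Working it through.** **Check of the plan's own figures.** The 90% Wilson interval for 15/50 is 20.6% to 41.5%, in line with the 21% to 41% that 14.3 gives for a 30% adverse event rate. Simulating the design in 14.1 (N = 50, exponential OS with median 9 months, uniform accrual over 18 months, 6 months more follow-up, Kaplan-Meier with log-scale Greenwood variance) gives 85.2% power for the 90% interval and 77.4% for the 95% interval, against the stated 85% and 78%.

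**Inputs.** N = 50 and the 9- and 5-month medians come from 14.1. Exponential survival, uniform accrual and the loss rates are my assumptions; the documents give no loss rate. With λ = ln 2 / 9 = 0.0770 per month, true OS12 = exp(−12λ) = 39.7%.

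**Case A: the analysis waits for planned follow-up.** Section 6.5 counts 12 months from stopping therapy, which cannot precede starting it, so every patient still under observation passes month 12. Only loss, withdrawal or early closure leaves status unknown. For a proportion d lost by month 12 (from loss or withdrawal alone):

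- loss hazard μ = −ln(1 − d)/12
- known alive A = exp(−12(λ + μ))
- unknown U = [μ/(λ + μ)] × (1 − A)
- counted dead: A; dropped: A/(1 − U); counted alive: A + U

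At d = 10%, μ = 0.00878, A = 0.357 and U = 0.066, so the three rules give 0.357, 0.357/0.934 = 0.382 and 0.357 + 0.066 = 0.423.

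| Assumed loss | Unknown of 50 | Counted dead | Dropped | Counted alive |
|---|---|---|---|---|
| 0% | 0 | 39.7% | 39.7% | 39.7% |
| 2% | 0.7 | 38.9% | 39.4% | 40.2% |
| 5% | 1.6 | 37.7% | 39.0% | 41.0% |
| 10% | 3.3 | 35.7% | 38.2% | 42.3% |

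The largest bias is 39.7 − 35.7 = 4.0 points. Dropping unknowns costs 0.3 to 1.5 points. For scale, the Wilson interval for 20/50 is 29.4% to 51.6%, a half-width of about 11 points. Simulated coverage of the nominal 90% interval at 2%, 5% and 10% loss is 88%, 87% and 83% (dead), 90%, 90% and 89% (dropped), and 89%, 89% and 86% (alive).

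**Case B: the analysis is run at 18 + 6 months.** Potential follow-up is uniform on 6 to 24 months, so one third of patients (16.7 of 50) have less than 12 months.

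- Unknown = [exp(−6λ) − exp(−12λ)]/(18λ) = (0.630 − 0.397)/1.386 = 0.168, or 8.4 of 50
- Known alive = (2/3) × 0.397 = 0.265, or 13.2 of 50
- Counted dead: 13.2/50 = 26%; dropped: 13.2/41.6 = 32%; counted alive: 21.6/50 = 43%

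Simulated coverage is 33%, 72% and 84%. At a 5-month median (true OS12 18.9%), 4.9 are unknown and the rules give 12.6%, 14.0% and 22.5%.

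**Check of the fix.** Let S be the Kaplan-Meier estimate at 12 months and V its Greenwood variance. Use Wilson limits with n_eff = S(1 − S)/V. With no censoring V = S(1 − S)/n, so n_eff = n and the interval is exactly the planned one. In simulation at a 9-month median, S averages 39.7% and the limits cover 89% to 90% in both cases, including every loss rate in the table.

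**The case against.** The best defence is that the planned follow-up suits a simple proportion. Sections 6.4 and 6.5 and Appendices E and F carry observed patients past month 12, 14.2 keeps patients removed from the efficacy cohort under survival follow-up unless they withdraw consent, and the quality-of-life summary expects 12-month survivors. All of this stands, and it is why the effect is small if the analysis waits. What remains is that no sentence says it waits, and that withdrawal and loss are possible with no rule attached.

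A reader might infer that OS12 will be badly biased, taking Case B as the plan. The documents do not support that: 18 + 6 months appears only as an assumption behind the power for median OS, and nothing makes it the analysis date.

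A reader might also infer that Wilson is the wrong interval and should give way to the log-scale Greenwood interval planned for OS. That does not follow. The text names an interval, not a point estimator, and Wilson limits can be put on a Kaplan-Meier estimate. With complete data the log-scale interval is somewhat wider: 30.1% to 53.2% against 29.4% to 51.6% at 20/50, and 23.8% to 67.3% against 22.3% to 60.7% at 6/15 (an assumed subgroup size). Switching is a preference with a cost in small PD-L1 subgroups.

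Finally, the Kaplan-Meier curve will be reported anyway, so a censoring-adjusted value is available. That limits the harm, but leaves two figures that may disagree.

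**Conclusion.** The gap is real and minor. OS12 is specified by an interval that ordinarily presumes complete month-12 status, with no cutoff and no rule for earlier censoring, beside a Kaplan-Meier analysis of the same data. If the analysis waits for planned follow-up, the bias is at most about 4 points at 10% loss with unknowns counted as dead, and 0.3 to 1.5 points at 2% to 10% loss with unknowns excluded. Only an analysis at 18 + 6 months would make it large. These sizes rest on exponential survival with a 9-month median, loss unrelated to prognosis, the assumed loss rates and, for the early cutoff, uniform accrual. OS12 is secondary with no decision threshold, and the primary conclusion on median OS is unaffected.

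**What to change.** In 14.3 and the synopsis, define OS12 as the Kaplan-Meier survival probability at 12 months, overall and by PD-L1 status. Keep the 90% Wilson interval, computed with n_eff = S(1 − S)/Greenwood variance; if the estimate is 0% or 100%, use the ordinary Wilson interval with n. Report the data cutoff and the number censored before month 12. Leave the response rate as it is.

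The cost is a sentence or two in each place and slightly more analysis work, with no extra data. Nothing is lost with complete follow-up, since the interval is then the one already planned. The change does not correct for withdrawal related to prognosis, so the count of patients censored before month 12 should stand beside the estimate.
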